In the multiple ascending dose part of the study the drug was given in doses of 30 mg, 70 mg and 120 mg once daily for 8 days. Twenty-seven subjects were randomised; 9 to placebo, and 6 to each of the dosing groups. No serious adverse events were reported; 47 non-serious adverse events were reported by 20 subjects. Again the majority of AEs were mild, 2 were moderate and one severe. The AEs considered to be moderate were headache (on 30 mg dose) and dyspepsia (on placebo). Severe AE was a headache on the 120 mg dose. Three subjects were withdrawn; one on the 30 mg dose because of asymptomatic nocturnal bradycardia, one on the 70 mg dose because of a run of premature atrial contractions, and one on the 120 mg dose because of headache, nausea and vomiting. The AEs on the 120 mg dose were deemed to be causally related to study drug. No significant laboratory or QT abnormalities were noted in this part of the study.

Overall, in this first administration to man study, AZD9668 was well tolerated except for the occurrence of headaches at the highest doses tested. The PK data from this study is detailed in Section 3.2.1.

Further details of the preclinical toxicology and pharmacology can be found in the Investigators Brochure.

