Patients will attend the CPU in fasted state with their BronkoTest[©] diary card on the morning of Day -1 and stay until Day 3. Eligibility will be re-confirmed and safety assessments performed (vital signs, ECG, lung function, haematology, clinical chemistry and urinalysis, urine drug screen including alcohol). Twenty-four hour ambulatory cardiac monitoring (telemetry) will be started on Day -1 and monitoring continued for 24 hours post first dose. All urine produced over the 24 hours before the first dose will be collected for assessment of baseline desmosine levels and for the pre-dose urine PK. [For all timed urine collections, the patients should empty the bladder within 10 minutes of Time 0, discard that urine and then collect all the urine from then onwards. At Time (0 + t hours) they should then empty the bladder and add that to the collection.] On the morning of Day -1, the patients will provide an induced sputum sample; weight of the sample will be recorded, and the sample processed for neutrophils and AZD9668 levels. Blood will also be collected for baseline assessment of hsCRP and serum amyloid A.

Patients will fast from midnight on Day 1 until 2 hours after the first dose (water will be allowed for thirst up until 1 hour before dosing).

On Day 1, pre-dose patients will be asked to provide a spontaneous sputum sample for quantitative bacteriology. They will be randomised to receive either AZD9668 or placebo: A single dose will be administered in the morning of Day 1. All urine produced over the 24 hours after the first dose will be collected for measurement of AZD9668 concentrations. Urine will be collected for time periods 0-4 hours, 4-12 hours and 12-24 hours. Aliquots from each of these collections will be taken for urine PK, and an aliquot from the pooled sample will be taken for urine desmosine. Serial blood samples will be collected for PK analysis at pre-dose and at 0.25, 0.5, 1, 2, 3, 4, 5, 6, 8, 12, and 24 hours post dose (NB. PK samples taken at 24 h will be taken pre-dose). Vital signs and ECG will be done at approximately 1 hour after the first dose.

On Days 2 - 13 the patients will receive 2 daily doses of AZD9668. The first dose of each day will be taken at approximately the same time $(\pm 1h)$ as the first dose administered on Day 1 and the 2nd daily dose will be approximately 12 hours later $(\pm 1 \text{ hour})$.

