Visit 4: End of Treatment (Days 14 & 15 ±1 day): Patients will attend the CPU with their BronkoTest[®] diary card and study medication on the morning of Day 14 in fasted state, having fasted from midnight (water will be allowed for thirst up until 1 hour before dosing) and having withheld taking their morning dose of study medication, and stay until the morning of Day 15. Blood will also be collected pre-dose for assessment of PK, hsCRP and serum amyloid A. Before administration of the morning dose on Day 14, safety assessments (vital signs, ECG, lung function, haematology, clinical chemistry, urinalysis and urine drug screen) will be performed. Patients will then take their morning dose of study medication in the CPU. This will be the final dose of study medication. At 1 hour post-dose, an ECG will be recorded. Approximately 1-2 hours after this last dose, patients will provide an induced sputum sample (around the same time they had the induced sample on Day -1); weight of the sample will be recorded, and the sample processed for neutrophils and AZD9668 levels.

All urine produced over the 24 hours after the last dose will be collected for measurement of desmosine levels and AZD9668 concentrations. Urine will be collected for time periods 0-4 hours, 4-12 hours and 12-24 hours. Aliquots from each of these collections will be taken for urine PK, and an aliquot from the pooled sample will be taken for urine desmosine. Serial blood samples will be collected for PK analysis at pre-dose and at 0.25, 0.5, 1, 2, 3, 4, 5, 6, 8, 12, and 24 hours post dose. On the morning of Day 15, a spontaneous sputum sample will be collected for quantitative bacteriology, and the patients will be discharged from the CPU with their BronkoTest[®] diary card to bring to their follow-up visit.

Visit 5: Follow-up (Day 21 ±3 days): Patients will return to the CPU with their BronkoTest[®] diary card in fasted state, having fasted from midnight (water allowed), for follow-up safety assessments (physical examination, vital signs, ECG, lung function, haematology, clinical

chemistry and urinalysis). A blood sample for hsCRP and serum amyloid A will also be collected at this visit.

Throughout the study, lung function measurements should be performed at the same time of day ± 2 hours in relation to the time point at Visit 1 (baseline).

Each patient will attend the visits as outlined in Figure 1.

[figure not shown]

Table 1Study plan

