	Screening visit	Study Visit (start) 2				Study visit	Study visit (end) 4		Follow- up 5
Study Visit	1					3			
Study Day	-21 to -8	-1	1	2	3	7 (±1)	14(±1)	15	21 (±3)
Residential stay ^a		~	~	~	~		~	~	
Informed consent	√								
Incl./Excl criteria	✓	✓							
Demographics	✓								
Med/surgical history	✓								
Drug screen including alcohol	✓	✓				✓	✓		
Virology	✓	1					1	1	
Pregnancy test /FSH (if appropriate)	~								
Concomitant medication	~	~	✓	~	✓	~	~	✓	~
Adverse event questioning		~	~	~	✓	~	✓	✓	✓
Randomisation			✓						
Dispense study drug					✓	✓			
Physical examination	✓								✓
Vital signs ^b	✓	✓	✓	✓	✓	✓	✓		✓
12-lead ECG ^b	✓	✓	✓	✓	✓	✓	✓		✓
Telemetry		✓	✓						
Safety blood/urinalysis ^c	✓	✓		✓		✓	✓		✓
Lung function ^c	✓	✓		✓		✓	✓		✓
Induced sputum ^d		✓					✓		
Quantitative sputum bacteriology ^e			~					~	
24-h urine collection for desmosine ^f		~					~		
Urine PK ^g		✓	✓				✓		
Plasma - full PK profile ^h			✓				✓		
Plasma– single PK sample ⁱ						✓			
Serum – hsCRP, amyloid-A		✓				~	✓		✓
Plasma for multiplex analysis of cytokines (including but not limited to TNF-α, IL-8)		~					~		✓

Table 1Study plan

	Screening visit (start)			Study visit	Study visit (end)		Follow- up		
Study Visit	1	2				3	4		5
Study Day	-21 to -8	-1	1	2	3	7 (±1)	14(±1)	15	21 (±3)
BronkoTest [©] diary card ^j	✓	~	~	~	~	~	✓	✓	~
Return study drug						~	~		
Non-residential visit	~					~			✓
Genetic blood sample ^k			~						

^a Patients to be resident in the CPU from the morning of Day -1 to the morning of Day 3, and from the morning of Day 14 to the morning of Day 15.

^b Vital signs & ECG to be taken at Screening visit, Day -1, Day 1 (1h after 1st morning dose), Days 2, 3 (prior to discharge), 7 and 14 (before morning dose), and at follow-up. An additional ECG will be recorded 1 hour post-dose in Day 14..

- ^c Safety blood, urinalysis & lung function (SVC, FEV₁, FVC, IC) to be done at Screening visit, Day –1, before morning dose on Days 2, 7 & 14, and at follow-up.
- ^d Induced sputum (for sputum weight, neutrophils, & AZD9668) to be done at visit 2 (Day -1)and 1-2 hours after the last dose on Day 14.
- ^e Quantitative sputum bacteriology to be done on a spontaneous sample (pre-dose on Day1), preferably that produced first thing in the morning.

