4.7.3.1 Methods of assessment

Vital signs

Vital signs comprise the assessment of systolic and diastolic blood pressure, pulse, respiratory rate and body temperature. Assessments of vital signs resulting in clinically significant abnormal values will be repeated, in order to exclude an erroneous assessment. Controls will also be necessary if implausible measurements occur, e.g., significant deviations from previous assessments. Individual results will be classified as 'normal', 'abnormal with no clinical significance' and 'abnormal with clinical significance'. Abnormal values 'with no clinical significance' may be considered clinically significant if they are accompanied by clinical symptoms such as dizziness, tiredness, nausea or vomiting etc.

All measurements of vital signs will be done according to the applicable SOP.

Twelve-lead ECG

Twelve-lead ECGs will be recorded in accordance with local procedure.

A resting ECG will be recorded at Visit 1 for confirmation of study eligibility and at Visit 5 for follow-up safety assessment. Further ECG recordings will be performed according to the study plan (Table 1). ECGs will be recorded in the supine position after the patient has rested in this position for at least 10 minutes. Only overall evaluation will be captured in Any abnormalities (including QTc values) should be reviewed by a cardiologist or an appropriately qualified person.

The original ECGs and variables must be signed and dated and stored in the patient's medical record as source data.

Telemetry

Ambulatory cardiac monitoring will be performed using CardioMem CM3000 recorders (Getemed, Germany) from 24 hours pre-dose to 24 hours post first dose at Visit 2. The Investigator or delegate will review and evaluate the recordings before dosing, and before discharge. A print-out will be signed and dated by the Investigator and filed with the CRF.

Physical examination

A full physical examination will be performed to ensure suitability according to the inclusion and exclusion criteria at the Screening visit. The physical examination comprises a routine medical examination including gross neurological assessments. Measurement of body weight and height will be done as well.

The physical examination will be repeated as the follow-up visit and any new findings should be recorded as adverse events.

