6.5 Determination of sample size

No formal statistical sample size calculation has been performed for this phase II trial. The number of patients included is based on feasibility.

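### Day 14 has a 12-lead ECG at 1 hour post-dose but no vital signs with it, so this primary tolerability measure has no timed reading near the steady-state peak

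*Protocol*

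**What the plan says.** Protocol Section 2.1 lists vital signs among the measures of tolerability over 14 days of dosing. Section 4.7.3.1 defines them as systolic and diastolic blood pressure, pulse, respiratory rate and body temperature.

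The schedule is in Section 3.1 and Table 1, footnote b:

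- **Day 1:** "Vital signs and ECG will be done at approximately 1 hour after the first dose".
- **Day 2:** before the morning dose.
- **Day 3:** before discharge, which follows the fourth dose. No interval from that dose is given.
- **Days 7 and 14:** "7 and 14 (before morning dose), and at follow-up".
- **Day 14, post-dose:** the Visit 4 text says "At 1 hour post-dose, an ECG will be recorded", and footnote b agrees: "An additional ECG will be recorded 1 hour post-dose in Day 14". Neither adds vital signs.

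Ambulatory cardiac monitoring runs "from 24 hours pre-dose to 24 hours post first dose at Visit 2" (Section 4.7.3.1) and is not repeated. Section 3.2.1 explains that patients are fasted on Days 1, 7 and 14 so that ECGs can be taken when the peak concentration is maximised.

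**The concern.** The protocol pairs vital signs with the ECG at 1 hour on Day 1, then repeats only the ECG at 1 hour on Day 14, and gives no reason for the difference. It accepts the principle of measuring near the peak, because it fasts patients for that purpose.

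As scheduled, the timed peak reading of vital signs describes a single dose. The readings with a fixed time on repeated dosing describe troughs. A concentration-related effect on blood pressure that is present at the steady-state peak and gone by the next dose would not be captured by any timed reading. The trial is meant to support longer studies in patients (Sections 1.2 and 3.2.1), so the steady-state peak is the condition of most interest.

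**Working it through.** There is no power or sample size figure to reproduce: Section 6.5 says "The number of patients included is based on feasibility", and the point does not depend on one. The check has two parts.

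**1. Which readings fall near a peak**

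| Day | Vital signs | 12-lead ECG |
|---|---|---|
| 1 | about 1 h post-dose | about 1 h post-dose |
| 2 | pre-dose | pre-dose |
| 3 | before discharge, untimed | before discharge, untimed |
| 7 | pre-dose | pre-dose |
| 14 | pre-dose only | pre-dose and 1 h post-dose |

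Section 3.2.1 gives a median steady-state tmax of 1 hour in volunteers, so the Day 14 ECG sits near the peak and the vital signs do not.

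**2. How far apart the concentrations are**

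Inputs: dose 60 mg on Day 1, b.i.d. on Days 2 to 13, once on Day 14 (Section 3.4.2); molecular weight 545.5 (Section 1.1); steady-state half-life and CL/F of 9.04 h and 14.7 L/h, 10.24 h and 14.8 L/h, 8.73 h and 19.4 L/h (Section 3.2.1). Assumptions: one compartment, first-order absorption with tmax = 1 h, doses exactly on schedule.

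Formulas: D = 60,000/545.5 = 110 µmol; k = ln 2 / half-life; V = (CL/F)/k; ka solves ln(ka/k)/(ka − k) = 1 h. Then:

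- Day 1 at 1 h = (D/V)·e^(−k)
- Day 14 pre-dose = (D/V)·[ka/(ka − k)]·e^(−12k)/(1 − e^(−12k))
- Day 14 at 1 h = Day 1 at 1 h + Day 14 pre-dose × e^(−k)

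Worked for 8.73 h and 19.4 L/h: k = 0.0794, V = 244 L, ka = 4.00. Day 1 at 1 h = (110/244) × 0.924 = 0.416 µM. Day 14 pre-dose = 0.450 × 1.020 × 0.386/0.614 = 0.288 µM. Day 14 at 1 h = 0.416 + 0.288 × 0.924 = 0.682 µM.

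| Half-life, CL/F | Day 1, 1 h (µM) | Day 14 pre-dose (µM) | Day 14, 1 h (µM) | Day 14 / Day 1 at 1 h | Pre-dose / 1 h on Day 14 |
|---|---|---|---|---|---|
| 8.73 h, 19.4 L/h | 0.416 | 0.288 | 0.682 | 1.64 | 0.42 |
| 9.04 h, 14.7 L/h | 0.531 | 0.387 | 0.890 | 1.68 | 0.44 |
| 10.24 h, 14.8 L/h | 0.470 | 0.408 | 0.851 | 1.81 | 0.48 |

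Over the wider single-dose half-life range in Section 3.2.1 (5.04 to 14.99 h), the Day 14 to Day 1 ratio at 1 h runs from 1.25 to 2.36. The direction is therefore stable; the size is not.

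**Checks on the model.** Daily AUC at steady state is (120,000/545.5)/(CL/F), which is 11.3 to 15.0 µM·h. This brackets the 18/1.4 = 12.9 µM·h implied by the protocol's exposure margin. The modelled Day 14 level of 0.68 to 0.89 µM lies below the 2.5/2.6 = 0.96 µM implied by the Cmax margin. The model also predicts 18 to 25% peak accumulation with once-daily dosing, where Section 3.2.1 reports none. The 1.6 to 1.8 ratio is therefore probably an upper-end figure.

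**Day 3.** In the same model, a reading 1 h after the fourth dose would be at 0.93 to 0.96 of the Day 14 1-hour level, and one taken just before that dose at 0.37 to 0.41. The protocol does not say which applies.

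**The case against.** Four points carry weight.

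- **The Day 14 ECG.** A 12-lead recording at 1 hour shows heart rate and rhythm near the peak. A reader might infer that pulse, blood pressure and rhythm are never observed at the highest exposure. The documents do not support that: at that time point the missing items are blood pressure, respiratory rate, temperature and a continuous recording. The ECG is brief, however, and Section 4.7.3.1 captures only an overall evaluation.
- **Day 3.** Its vital signs may well follow the fourth dose at close to steady-state levels. Because the timing is open, this softens the gap but does not close it.
- **Rhythm.** A reader might infer that the 24-hour recording must be repeated at steady state, since one volunteer on repeated dosing was withdrawn for nocturnal bradycardia and another, "one on the 70 mg dose because of a run of premature atrial contractions". Section 3.2.2 weighs such events, finds no consistent pattern or dose-response, links them to baseline abnormalities and responds by exclusion. Amendment 01 tightens the ectopic limit and adds cardiac exclusions and QTcF criteria. A repeat recording is a preference, not a correction.
- **Placebo control.** A reader might infer that an effect would appear to fade by construction. No Day 1 versus Day 14 comparison is specified, and Section 6.4.4 compares the arms informally at the same nominal times. What remains is narrower: on Day 14 the vital-signs comparison between arms is itself made at trough.

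It is also fair that the schedule is internally consistent on these time points. Volunteers have already received 120 mg once daily for 8 days, which the same model puts at a peak of 0.98 to 1.27 µM, about 1.4 times the Day 14 peak here. That reduces the concern about exposure in general, but it does not supply readings in patients with COPD.

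**Conclusion.** The point holds in a limited form. Vital signs have no timed post-dose reading at steady state, while the ECG does. The Day 14 reading is taken at about 42 to 48% of the modelled 1-hour level that day, and the only timed peak reading is at a level lower than the Day 14 peak by a factor of about 1.6 to 1.8, probably an upper-end figure. The schedule facts need no assumption. The sizes rest on a one-compartment model with healthy-volunteer parameters and a 1-hour tmax, and patients with COPD may differ. This is an inexpensive improvement to a primary tolerability measure. It does not show that the trial leaves heart rate or rhythm unobserved at steady state.

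**What to change.** In Table 1, footnote b, and in the Visit 4 text of Section 3.1, add vital signs at 1 hour post-dose on Day 14, taken with the ECG already scheduled then. State that they precede the sputum induction planned for about 1 to 2 hours after the dose, so that the reading is comparable with Day 1, when no induction is scheduled. Summarise the Day 14 1-hour value by treatment alongside the Day 1 1-hour value, separately from the pre-dose visits; the layout can go in the SAP.

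Cost: a small amendment, a few minutes and one more set of readings per patient, at most 18 in all. The patient is already resident and supine for the ECG, and no visit or blood sample is added.

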3.2 Rationale and risk/benefit assessment

3.2.1 Rationale for study design, doses and control groups

Patients with COPD are the target population for the NE inhibitor AZD9668. The main purpose of this study is to establish the tolerability of AZD9668 in patients with COPD as a preliminary to long-term proof-of-concept studies in this population. It is also intended to get pharmacokinetic (PK) data in this population that would help in the planning of future patient studies. So far safety/tolerability and PK data are available in healthy volunteers up to 150 mg as a single dose and up to 120 mg daily for 8 days as multiple doses. A 14-day study in 12

patients with COPD on active treatment is deemed sufficient to establish tolerability in a patient population, before proceeding to longer-term studies in patients with COPD.

The first-in- man, two-part, single and multiple ascending dose (SAD and MAD) study of AZD9668 in healthy volunteers (D0520C00001) is now complete and the reporting phase is underway. In the SAD part of the study the doses that have been safely administered were 2, 10, 30, 60, 120 and 150 mg. Dose escalation was stopped because the exposure limits set by the internal AstraZeneca Human Exposure Limits Committee (HELC) were reached. These limits (i.e. $AUC_{(0-24h)}$ and C_{max} of 18 µM.h and 2.5 µM, respectively) were set following a review of the data obtained in the 1-month toxicology studies in the rat and dog and have been based upon the exposures at the no observed adverse effect level (NOAEL) in rat (370 mg/kg), corrected for the differences in plasma protein binding between the species. The NOAEL in the rat has been used because the free exposures at this dose are lower than those obtained in the dog at the no observed effect level (NOEL) dose. In the MAD part of the study the doses that have been safely administered were 30, 70 and 120 mg once a day for a total of 8 days.

Following single dose administration of AZD9668 (2 - 150 mg) absorption was rapid, median t_{max} ranged from 1h to 2h. The geometric mean CL/F ranged from 15.4 to 21.6 L/h and the geometric mean V_z /F ranged from 157 to 334L. The geometric mean terminal half-life of AZD9668 ranged from 5.04 to 14.99h. The CL/F, V_z /F and $t_{1/2}$ appeared to be independent of dose. The exposure (C_{max} and AUC) increased proportionally with dose between doses of 10mg and 150mg.

AZD9668 is renally eliminated and renal clearance (CL_R) and the percentage of the dose excreted as unchanged AZD9668 in the urine over 48 h ($F_{e(0-48)}$ (%)) appeared to be independent of dose. The geometric mean CL_R ranged from 5.83 L/h to 6.98 L/h, and the range of the geometric mean $F_{e(0-48)}$ (%) was 31.6 % to 40.0 %.

Following multiple dose administration of AZD9668 (30 mg, 70 mg and 120 mg, once a day for 8 days), absorption was similar following single and multiple dosing; the median t_{max} and $t_{max,ss}$ was 1h for all dose groups. The geometric mean CL/F_{,ss} was 14.7, 14.8 and 19.4 L/h and the geometric mean Vz/F_{,ss} was 191L, 218 and 245L, respectively. The geometric mean $t1/2_{,ss}$ was 9.04h, 10.24h and 8.73h, respectively, and there was no evidence for time or dose dependent change in PK. There was no evidence of accumulation upon multiple dosing to steady state.

AZD9668 is renally eliminated and renal clearance at steady state ($CL_{R,ss}$) and the percentage of the dose excreted as unchanged AZD9668 in the urine at steady state over 48 h ($F_{e(0-48),ss}$ (% dose)) appeared to be independent of dose. The geometric mean $CL_{R,ss}$ was 5.29 L/h, 5.70 L/h and 5.83 L/h, and the geometric mean $F_{e(0-48),ss}$ (% dose) was 38.8 %, 40.9 % and 31.6 %, respectively.

Administration of AZD9668 after consumption of a high fat meal resulted in a reduction in the rate of absorption (median t_{max} was 4 h, 3 h and 4 h for 30 mg, 70 mg and 120 mg, respectively). The C_{max} was reduced by 22 %, 31 % and 22 % and the AUC_(0-24h) was slightly

reduced, by 8 %, 5 % and 5% for 30 mg, 70 mg and 120 mg, respectively. Thus consumption of the food reduced the rate but had relatively little effect on the overall extent of absorption.

A population PK model of the PK data from the SAD and MAD study has been developed and was used to estimate the mean population PK parameters of AZD9668 with the associated variability and to assess the affect of consumption of a high fat breakfast on the PK of AZD9668. A dose of 60 mg twice a day has been selected as the dose for the current study. This dose has been chosen as a dose that is predicted to achieve trough steady state therapeutic plasma concentrations of 19 nM (predicted from an in vivo mouse acute lung injury model) in all patients, whilst ensuring that the predicted geometric mean Cmax,ss and AUC(0-24h),ss are below the HELC limits. The estimated margins to the HELC limits in the fasted state are 2.6 and 1.4 for C_{max,ss} and AUC_{(0-24h),ss}, respectively, and this will be the dose that will be used in the subsequent proof-of-principle studies with AZD9668. If a dose of 60 mg b.i.d is not tolerated by an individual patient then his/her dose may be halved to 30 mg b.i.d for the remainder of the study, at the investigator's discretion. The population PK model predicts that this will still achieve trough steady state plasma concentrations above 19 nM in all the patients. Since the objective of the study is to investigate tolerability, the higher dose (i.e. 60 mg b.i.d) has been chosen as the study dose rather than the minimum dose that is predicted to achieve therapeutic exposures. AZD9668 will only be dosed once a day on Days 1 and 14 to enable measurement of single dose and steady state pharmacokinetics respectively.

From the population PK modelling it was identified that the bioavailability of AZD9668 was approximately 90% of that when it was administered in the fasted state. This did not however have any impact upon the dose selection. For the subsequent studies therefore, it is not necessary for the patients to restrict food around administration of their doses.

Patients will receive their morning dose in a fasted state on Days 1, 7 and 14, i.e. on days when they are having ECG measurements. This ensures that the ECG measurements can be taken when C_{max} is maximised.

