3. STUDY PLAN AND PROCEDURES

3.1 Overall study design and flow chart

This Clinical Study Protocol has been subjected to a peer review according to AstraZeneca standard procedures.

This study is a randomised, double-blind, placebo-controlled, parallel-group, single-centre study to evaluate the tolerability and pharmacokinetics of AZD9668 administered for 14 days in patients with moderate to severe COPD (GOLD stages II and III). 18 patients will be randomly assigned to receive either AZD9668 or matching placebo orally (in a ratio of 2 active: 1 placebo). On Day 1 patients will receive a single morning dose of 60 mg of AZD9668 (or matching placebo) for single dose PK. This will be followed by daily doses of 60 mg bid (twice daily, 12 hours apart) on Days 2 to 13 and finally a single morning dose of 60 mg on Day 14 for steady state PK.

The study will consist of 5 visits.

Patients must provide full written informed consent before any study-related procedures, restrictions or screening assessments are carried out.

Visit 1: Screening visit (Day –21 to Day –8): At Visit 1, after having given written informed consent, patients will be enrolled into the study and screened for eligibility (Table 1). If eligibility is confirmed at Visit 1, patients will be issued with a BronkoTest[®] diary card (to be completed daily for the remainder of the study) and asked to return to the CPU at Visit 2.

Visit 2: Treatment Period (Day –1 to Day 3): The day before dosing is defined as Day –1 and the day of dosing as Day 1, Day 0 does not exist.

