- ^f Urine for desmosine will be collected during the following periods: 24 h period before the first dose (Days -1 to 1) and 24 h period after the last dose (Days 14-15). For the latter, when it coincides with the urine PK, the timed PK samples will be pooled to take an aliquot for urine desmosine.
- ^g For urine PK aliquots will be taken from samples collected for the following periods: 0-4 hours, 4-12 hours and 12-24 hours. On Day -1 only, an aliquot will be taken from the 24-hour collection for the pre-dose sample.
- ^h Serial PK plasma samples to be taken pre-dose and 0.25, 0.5, 1, 2, 3, 4, 5, 6, 8, 12, and 24 hours after the first and last dose (i.e. on Days 1-2 and 14-15). NB the sample taken at 24 hours on Day 2 will be taken pre-dose.
- ⁱ Plasma PK sample taken pre-dose
- ^j BronkoTest[©] diary card to be completed daily by patient throughout the entire study period.
- ^k If consent is not obtained at Visit 1, it can be obtained at any of the subsequent visits. Sampling is planned for the randomisation visit, but can be taken at a subsequent visit

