3.4.2 Doses and treatment regimens

In the current study the daily dose will be 120 mg (i.e. 60 mg b.i.d), except for days 1 and 14 when patients will receive only the morning dose to allow assessment of PK. This dose has been chosen as a dose that is predicted to achieve trough steady state therapeutic plasma concentrations of 19 nM (predicted from an in vivo mouse acute lung injury model) in all patients, whilst ensuring that the predicted geometric mean $C_{max,ss}$ and $AUC_{(0-24)ss}$ are below the HELC limits. The estimated margins to the HELC limits are 2.6 and 1.4 for $C_{max,ss}$ and $AUC_{(0-24)ss}$, respectively, in the fasted state. If a dose of 60 mg b.i.d is not tolerated by an individual patient then his/her dose may be halved to 30 mg b.i.d for the remainder of the study, at the investigator's discretion. The population PK model predicts that this will still achieve trough steady state plasma concentrations above 19 nM in all patients.

For morning doses administered on Days 1, 7 and 14, patients will be fasted from midnight the night before dosing except water for thirst. The patients may consume water up to 1 hour before dosing. The dose will be administered with 240 mL of water, and the patients must drink all the water. The patients must not consume any further fluids or food for a minimum of 2 hours post dose. At this time the patients will be allowed a light breakfast. Fasting the patients prior to receiving their morning dose on days when they are having ECG measurements ensures that the ECG measurements can be taken when C_{max} is maximised. There is no requirement to restrict food consumption before or immediately after administration of the remaining doses. These doses can be administered with approximately 100 mL water.

The morning and evening doses will be filled individually in high-density polyethylene (HDPE) bottles with a child resistant cap according to the random scheme. All bottles for morning and evening dose for 14 days will be packed in a white box for each patient.

At Visit 2, the required number of bottles needed for the morning and evening dose until Visit 3 will be handed over to the patient after the 4th dose has been taken in the CPU.

At Visit 3, the required number of bottles until Visit 4 will be handed over to the patient after the morning dose has been administered.

At Visit 4, the patient will be administered the morning dose in the CPU by the staff.

[figure not shown]

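### The Day 14 AUC(0-24),ss covers one 60 mg dose but carries the symbol used for two-dose daily exposure, and falls short of that exposure by roughly 30%

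*Protocol*

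**What the plan says.** The regimen is set out in Protocol Section 3.4.2: "In the current study the daily dose will be 120 mg (i.e. 60 mg b.i.d), except for days 1 and 14". Section 3.1 describes the last day as "finally a single morning dose of 60 mg on Day 14 for steady state PK", and Section 3.2.1 gives the reason: "AZD9668 will only be dosed once a day on Days 1 and 14 to enable measurement of single dose and steady state pharmacokinetics respectively". Under footnote h of Table 1, plasma is sampled pre-dose and at intervals including "1, 2, 3, 4, 5, 6, 8, 12, and 24 hours after the first and last dose".

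The synopsis and Section 4.5.2 list AUC(0-24),ss among the Day 14 parameters. Section 4.5.2 also uses it as the numerator of the accumulation ratio Rac. The abbreviation list defines AUC(0-24) as running from time zero to 24 hours after the dose. Neither list has a 12-hour dosing-interval area for Day 14.

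The same symbol appears in the dose rationale. The AUC(0-24h) and Cmax limits set by the sponsor's exposure committee (HELC) are "18 µM.h and 2.5 µM, respectively". The 60 mg twice-daily dose was chosen "whilst ensuring that the predicted geometric mean Cmax,ss and AUC(0-24h),ss are below the HELC limits". Section 3.2.1 continues: "The estimated margins to the HELC limits in the fasted state are 2.6 and 1.4 for" Cmax,ss and AUC(0-24h),ss respectively.

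**The concern.** One symbol stands for two quantities. In Sections 3.2.1 and 3.4.2 it is the predicted daily exposure on 60 mg twice daily. In the synopsis and Section 4.5.2 it is a measured area over 24 hours in which the evening dose is left out, so hours 12 to 24 show only decline.

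Plasma pharmacokinetics is a primary objective (Section 2.1), and Day 14 gives the trial's only full profile after repeated twice-daily dosing. The earlier multiple-dose data in Section 3.2.1 come from once-daily dosing. The same section says the dose will be carried into later studies and that in the first-in-man study "Dose escalation was stopped because the exposure limits set by the internal AstraZeneca Human Exposure Limits Committee (HELC) were reached". AUC has the tighter of the two margins. A reported Day 14 value with the symbol, time window and units of the limit invites a comparison for which it is the wrong quantity.

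**Working it through.** **Inputs, all from the protocol.** Molecular weight 545.5 g/mol (Section 1.1). From Section 3.2.1: AUC limit 18 µM.h; stated AUC margin 1.4; CL/F 15.4 to 21.6 L/h after single doses and 14.7, 14.8 and 19.4 L/h after multiple doses; half-life 9.04, 10.24 and 8.73 h at steady state (30, 70 and 120 mg once daily) and 5.04 to 14.99 h after single doses.

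**Step 1: reproduce the margin of 1.4.**
- Dose: 60 mg / 545.5 g/mol = 110 µmol, so 220 µmol a day.
- Predicted AUC implied by the margin: 18 / 1.4 = 12.86 µM.h.
- Implied CL/F with two doses: 220 / 12.86 = 17.1 L/h. This value is back-solved and is not printed in the protocol, but it lies inside the reported 14.7 to 21.6 L/h. Those two ends give margins of 1.20 and 1.77.
- If 12.86 µM.h were instead the Day 14 one-dose area defined in Step 2, CL/F would have to be 110 × 1.398 / 12.86, or about 12 L/h, which is outside the reported range.

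The rationale therefore means two doses.

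**Step 2: what Day 14 measures.** Let D be one dose and f the share of a single-dose AUC lying beyond 12 h. At steady state on 12-hourly dosing:
- area from 0 to 12 h = D/CL;
- area from 12 to 24 h with the evening dose omitted = f × D/CL;
- true daily exposure = 2D/CL;
- measured / true = (1 + f)/2.

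For one compartment, f = exp(−12 ln 2 / t½). The last two columns take the true daily AUC as 12.86 µM.h.

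| t½ (h) | Source | f | (1 + f)/2 | Shortfall | Day 14 area (µM.h) | Apparent margin |
|---|---|---|---|---|---|---|
| 8.73 | multiple dose, 120 mg | 0.386 | 0.693 | 30.7% | 8.91 | 2.02 |
| 9.04 | multiple dose, 30 mg | 0.398 | 0.699 | 30.1% | 8.99 | 2.00 |
| 10.24 | multiple dose, 70 mg | 0.444 | 0.722 | 27.8% | 9.28 | 1.94 |
| 5.04 | single dose, shortest | 0.192 | 0.596 | 40.4% | 7.66 | 2.35 |
| 14.99 | single dose, longest | 0.574 | 0.787 | 21.3% | 10.12 | 1.78 |

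**Step 3: check on the actual schedule.** Simulating one dose on Day 1, two a day on Days 2 to 13 and one on Day 14, with CL/F 17.1 L/h and absorption peaking at 1 h, gives ratios of 0.697, 0.703 and 0.726 at half-lives of 8.73, 9.04 and 10.24 h. The apparent margins are 2.01, 1.99 and 1.93. In each run 2 × AUC(0-12) on Day 14 returns 12.86 µM.h, the true daily exposure.

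**Step 4: the accumulation ratio.** Day 1 AUC(0-24) is (D/CL)(1 − f²) in this model, so Rac = (1 + f)/(1 − f²) = 1/(1 − f). That is the ordinary accumulation ratio for a 12-hour interval. Rac compares one-dose windows like for like and is not damaged.

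**The case against.** The strongest reply is that no consequence is written into the plan. The HELC margin appears only as a prediction supporting the dose. Section 6.4.2 plans descriptive summaries and no margin. The stopping criteria in Section 3.3.5.1, including those added by Amendment 01, are laboratory and QTcF rules, and Section 3.2.1 already names the dose for later studies. All of this stands. A reader might infer that the trial will declare a falsely wide safety margin. The documents do not support that, because they nowhere commit to comparing the Day 14 area with 18 µM.h.

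The single Day 14 dose is also openly stated, and it is useful: it leaves an uninterrupted 24-hour decline for the terminal half-life and a 24-hour urine collection after one dose. That stands too and is a reason to keep the design. Disclosing the schedule does not, however, separate the two meanings of the symbol.

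A reader might also take C24,ss to be offered as a steady-state trough. It is not. The abbreviation list gives that role to the pre-dose Cmin,ss, which is planned for Days 7 and 14. C24,ss needs only a clearer label.

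Finally, the parameter list in Section 4.5.2 is not closed, and a statistical analysis plan that is not shown here could add AUC(0-12),ss. That is possible. The point rests on what the protocol itself fixes, namely a one-dose area named as the regimen's 24-hour steady-state exposure. The listed AUCss does not fill the gap, since the abbreviation list defines AUC as running to infinity.

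**Conclusion.** The point holds as a mislabelled primary pharmacokinetic parameter. The Day 14 AUC(0-24),ss is not the daily steady-state exposure of 60 mg b.i.d. Under linear one-compartment kinetics it understates that exposure by about 28 to 31% at the multiple-dose half-lives and by 21 to 40% over the single-dose range. Only if it were compared with the HELC limit would a true margin of 1.4 appear as about 1.9 to 2.0 (1.8 to 2.35 over the single-dose half-lives).

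These sizes assume linear kinetics, one-compartment decline, healthy-volunteer half-lives that carry over to patients, and a prediction of exactly 12.86 µM.h. A marked distribution phase would make f smaller and the shortfall larger. The bound is f = 0, a shortfall of 50%. The documents give no parameters from which to fix a value in between.

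Nothing here shows that the limit would be exceeded or that the regimen is unsuitable. Severity: should-fix.

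**What to change.** - Add AUC(0-12),ss to the Day 14 parameters in the synopsis and Section 4.5.2, using the 12-hour sample already scheduled.
- Report 2 × AUC(0-12),ss as the daily steady-state exposure, and state that it reflects fasted dosing. Evening doses carry no food restriction (Section 3.4.2), and Section 3.2.1 puts bioavailability with food at about 90% of fasted, so the doubled value may slightly overstate actual daily exposure. The 1.4 margin is also quoted for the fasted state, so the two are comparable.
- Use only that value in any comparison with the HELC AUC limit.
- Relabel the Day 14 AUC(0-24) and C24 as values after the last single dose. AUC(0-24) may stay in Rac, described as a ratio of one-dose windows.

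The cost is wording in the synopsis, the abbreviation list and Sections 4.5.2 and 6.4.2, plus one derived parameter. No dose, visit or sample changes.
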